9.3.3 SAFETY ANALYSES

The safety analysis will be based on the as-treated population. The incidence of ADR/ADEs and changes in baseline in vital signs, clinical laboratory parameters, physical examination findings, ECOG performance status, will be analyzed as data are available.

The information contained in this protocol and all other information relevant to this study are confidential and proprietary information of Strata Oncology Inc., except as may be required by federal, state or local laws or regulation, and may not be disclosed to others without prior written permission of Strata.

Page 47 of 56

9.3.4 BIOMARKER ANALYSES

If relevant data are available, relationships between biomarkers, biomarker changes and clinical outcomes may be explored.

9.3.5 BASELINE DESCRIPTIVE STATISTICS

Descriptive statistics will be used to summarize the analysis dataset based on all available clinical and biomarker data. For available quantitative measures such as age or biomarker expression values, the mean, median, standard deviation, minimum and maximum will be tabulated.

For the quantitative measures, histograms and/or side-by-side boxplots will be presented and used to evaluate the underlying form of the distribution as well as the presence of any extreme values. It is important to ensure that the analysis is robust to identify a small number of outlying, extreme values or skewed data distributions. For expression data, log transformations are commonly used to create more symmetric data out of distributions that are skewed right. Presentation of histograms before and after transformations are useful to gauge the appropriateness of the transformation.

9.3.6 PLANNED INTERIM ANALYSES

For each cohort, 12 participants will be enrolled initially. If there is one response or no responses in these 12 participants as defined by CR or PR (for tdMeta) and ctDNA response (for μ Meta), the study will be stopped in that cohort. A minimum rwRR/ctDNA response of 10% and risk-benefit profile that the sponsor deems promising will be required before an additional 23 participants will be accrued for a total of 35 participants.

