HER2	Human epidermal growth factor 2
IB	Investigator's Brochure
ICF	Informed consent form
ICH	International Conference on Harmonization
IEC	Independent ethics committee
IND	Investigational New Drug
IRB	Institutional Review Board
iRECIST	Response Evaluation Criteria in Solid Tumors in cancer immunotherapy trials
ITT	Intent to treat
LDH	Lactate dehydrogenase
LVEF	Left ventricular ejection fraction
MITT	Modified intent to treat
mL	Milliliter
MSI	Microsatellite instability
MSI-H	Microsatellite instability-high
NCI	National Cancer Institute
NSCLC	Non-small cell lung cancer
NTRK	Neurotrophic receptor tyrosine kinase
OHRP	Office for Human Research Protections
ORR	Objective response rate
OS	Overall survival
PD-1	Programmed death receptor-1
PD-L1	Programmed death-ligand 1
PI	Principal Investigator
PR	Partial response

The information contained in this protocol and all other information relevant to this study are confidential and proprietary information of Strata Oncology Inc., except as may be required by federal, state or local laws or regulation, and may not be disclosed to others without prior written permission of Strata.

Page 9 of 56

QC	Quality control
RECIST	Response Evaluation Criteria in Solid Tumors
RNA	Ribonucleic acid
rwRR	Real world response rate
SAE	Serious adverse event
SAP	Statistical Analysis Plan
SOA	Schedule of Activities
SOC	Standard of care
SOP	Standard Operating Procedure
tdMeta	Traditionally defined/advanced metastatic
TIA	Transient ischemic attack
TTD	Time to treatment discontinuation
TTnT	Time to next treatment
UP	Unanticipated problems
US	United States
VAF	Variant allele frequency

The information contained in this protocol and all other information relevant to this study are confidential and proprietary information of Strata Oncology Inc., except as may be required by federal, state or local laws or regulation, and may not be disclosed to others without prior written permission of Strata.

Page 10 of 56

STATEMENT OF COMPLIANCE

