3 OBJECTIVES AND ENDPOINTS

3.1 OBJECTIVES AND ENDPOINTS

All endpoints will be assessed independently for each biomarker-defined cohort. **Tables A and B** list the objectives and endpoints for this study. Cohorts are stratified based on disease

The information contained in this protocol and all other information relevant to this study are confidential and proprietary information of Strata Oncology Inc., except as may be required by federal, state or local laws or regulation, and may not be disclosed to others without prior written permission of Strata.

Page 19 of 56

severity: (1) traditionally defined metastatic/advanced (tdMeta), and (2) micro-metastatic (μ Meta).

Table A: StrataPATH Objectives and Endpoints for tdMeta Cohorts

tdMeta Cohorts	
OBJECTIVES	ENDPOINTS
Primary	
Assess the clinical activity of anti-cancer therapies in participants with pre-specified biomarker profiles.	ORR – Overall Response Rate is defined as the percentage of participants with a best overall response of CR or PR based on Response Evaluation Criteria in Solid Tumors (RECIST) 1.1, as assessed by the investigator.
Secondary	
Assess the duration of response in anti-cancer therapies in participants with pre-specified biomarker profiles.	
 DoR – Duration of response is defined as the time from first documentation of disease response (CR or PR) until first documentation of progressive disease. TTD – Time to treatment discontinuation is defined as length of time from the date the participant initiates the systemic treatment to the date the participant discontinues treatment TTnT – Time to next treatment is defined as the length of time from the date the participant initiates study treatment to the date the participant initiates their next systemic treatment or death.
Evaluate ctDNA response rate at timepoints for participants who received anti-cancer therapies with pre-specified biomarker profiles.	ctDNA response – Proportion of participants with a <50% ratio of mean VAF will be defined as ctDNA responders. Molecular response is calculated as a ratio of mean VAF on-treatment at different timepoints compared to their baseline VAF.
Evaluate overall survival (OS) for participants who received an anticancer therapy with pre-specified biomarker profiles.	OS – Time from initiation of treatment until death from any cause.
Monitor and characterize the overall safety in the biomarker cohorts	The incidence of serious adverse events (SAEs).
Exploratory	

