9 STATISTICAL CONSIDERATIONS

9.1 SAMPLE SIZE DETERMINATION

The information contained in this protocol and all other information relevant to this study are confidential and proprietary information of Strata Oncology Inc., except as may be required by federal, state or local laws or regulation, and may not be disclosed to others without prior written permission of Strata.

Page 45 of 56

The study design is similar to a basket trial with each basket molecularly defined. For both cohorts (tdMeta and μ Meta), sample size calculations were completed under the following assumptions:

- Each cohort will enroll unique participants. Although participants may qualify for enrollment in more than one cohort, they will be enrolled in only one biomarker cohort (Refer to Section 10.2 for definitions).
- Each molecularly defined cohort will be evaluated independently.
- tdMeta and μ Meta cohorts will be evaluated independently.

Sample size was determined using a two-stage design based on minimizing the risk of a false negative result. The binomial probability of observing an exact number of responses was used similar to that in a Simon's two-stage design.^{19,20} The null hypothesis that the true response rate is 0.05 will be tested against a one-sided alternative. In the first stage, 12 patients will be accrued per cohort. If there are 1 or fewer responses in these 12 patients, the study will be stopped for that cohort. Response will be defined as partial response or complete response for tdMeta cohorts and <50% ctDNA mean VAF ratio for μ Meta cohorts. Otherwise, 23 additional patients will be accrued for a total of 35. The null hypothesis will be rejected if 6 or more responses are observed in 35 patients. This design yields a type I error rate of 0.001 and a power of 88% when the true response rate is 0.30.

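### Sections 9.1 and 9.3.6 state different rules for opening stage 2: the second adds an undefined response measure and a sponsor judgement that the quoted operating characteristics do not cover

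*Protocol*

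**What the plan says.** Section 9.1 sets out a two-stage rule. The hypothesis is given as "The null hypothesis that the true response rate is 0.05 will be tested against a one-sided alternative". Stage 1 takes 12 participants in each cohort, with this stopping rule: "If there are 1 or fewer responses in these 12 patients, the study will be stopped for that cohort". For a cohort that does not meet that stop, the text reads: "Otherwise, 23 additional patients will be accrued for a total of 35". The final decision is: "The null hypothesis will be rejected if 6 or more responses are observed in 35 patients". Response means PR or CR in tdMeta cohorts and a ctDNA mean VAF ratio below 50% in μMeta cohorts. The section gives a type I error of 0.001 and a power of 88% at a true rate of 0.30, and says the design aims to keep the risk of a false negative low.

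Section 9.3.6 covers the same look. It repeats the stop at 0 or 1 of 12, on the same response definitions, and then says: "A minimum rwRR/ctDNA response of 10% and risk-benefit profile that the sponsor deems promising will be required" before the further 23 are accrued.

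The term rwRR occurs in one other place, the List of Abbreviations, where it is spelled out as "Real world response rate". The tdMeta primary endpoint in Table A (section 3.1) is ORR, the "percentage of participants with a best overall response of CR or PR" by investigator RECIST 1.1. Neither Table A nor Table B lists a real-world response rate, and section 3.2 names only TTnT and TTD as real-world endpoints.

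**The concern.** Both sections are current text and govern the same decision. Under 9.1 a cohort with 2 responses in 12 goes on to 35. Under 9.3.6 the same cohort may be closed, either because rwRR falls below 10% or because the sponsor does not find the risk-benefit balance promising.

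The rwRR part affects tdMeta cohorts only, since ctDNA response is defined for μMeta cohorts. The sponsor condition affects both kinds.

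Two things are at stake. First, someone running the interim look cannot tell which rule applies or, for tdMeta, what to count. Second, the operating characteristics in 9.1 are those of automatic continuation. A design meant to avoid false negatives carries an extra gate that can only add them, with no size stated. The same text governs every cohort, and the Synopsis plans 20 cohorts of 35.

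**Working it through.** **Inputs (section 9.1).** n1 = 12; stop at 1 or fewer; 23 more for a total of 35; reject at 6 or more; p0 = 0.05, p1 = 0.30; stated type I error 0.001 and power 88%.

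**Step 1: the plan's own figures under automatic continuation.**

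P(reject) = Σ over x = 2 to 12 of P(X1 = x | 12, p) × P(X2 ≥ 6 − x | 23, p), where the second factor is 1 for x ≥ 6.

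| Stage-1 responses x | p = 0.30: P(X1 = x) × P(X2 ≥ 6 − x) | p = 0.05: P(X1 = x) × P(X2 ≥ 6 − x) |
|---|---|---|
| 2 | 0.16779 × 0.94616 = 0.15876 | 0.09879 × 0.02581 = 0.00255 |
| 3 | 0.23970 × 0.98431 = 0.23594 | 0.01733 × 0.10517 = 0.00182 |
| 4 | 0.23114 × 0.99703 = 0.23045 | 0.00205 × 0.32058 = 0.00066 |
| 5 | 0.15850 × 0.99973 = 0.15845 | 0.00017 × 0.69264 = 0.00012 |
| 6 or more | 0.11785 | 0.00001 |
| **Sum** | **0.9014** | **0.0052** |

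The stated figures are not reproduced. Power is 90.1% rather than 88%. Type I error is 0.0052 rather than 0.001, about five times as large. Changing only the final cut-off to 7 or more of 35 gives 0.0012 and 87.5%, which round to the stated values.

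**Step 2: does the 10% bar add anything if rwRR means ORR?** 10% of 12 is 1.2, so at least 2 responses are needed: 1/12 = 8.3% fails and 2/12 = 16.7% passes. The cut-off is the same as in 9.1, so type I error stays at 0.0052 and power at 90.1%.

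**Step 3: if rwRR is a different measure.** The documents give no way to score it, so no effect can be derived. As an illustration only, suppose each CR/PR in stage 1 is also recorded as a real-world response with probability s, and no extra real-world responses occur. Continuation then needs 2 or more on both counts, so each term in Step 1 is multiplied by P(Bin(x, s) ≥ 2). Power at p = 0.30 becomes 86.4%, 81.2%, 74.4% and 65.8% for s = 0.9, 0.8, 0.7 and 0.6. These values of s are assumptions.

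**Step 4: the sponsor condition.** Let g be the probability that the sponsor lets a cohort with 2 or more of 12 continue, assumed independent of the count. Power = 0.9014 × g and type I error = 0.0052 × g.

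| g (assumed) | Power | Type I error |
|---|---|---|
| 1.00 | 90.1% | 0.0052 |
| 0.95 | 85.6% | 0.0049 |
| 0.90 | 81.1% | 0.0046 |
| 0.80 | 72.1% | 0.0041 |
| 0.50 | 45.1% | 0.0026 |

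If refusal instead tracked the count, and cohorts with exactly 2 of 12 were always closed, the x = 2 row drops out: power 0.9014 − 0.1588 = 0.743 and type I error 0.0052 − 0.0026 = 0.0026. The protocol gives no value for g. Only the direction is certain: an added requirement lowers both quantities.

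**The case against.** The strongest reply is that this is loose wording. In 9.3.6 one sentence pairs CR/PR with ctDNA response and the next pairs rwRR with ctDNA response in the same order. No section describes collecting a separate real-world response, so rwRR is most plausibly a slip for ORR. That is likely, and on that reading the bar is harmless. But the document does not say so, and the abbreviation list expands the term as something other than ORR.

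A second reply is that discretion is disclosed. The Synopsis and section 4.1 allow cohorts to be discontinued, section 11.2 lists unacceptable risk and futility as grounds for termination, and two-stage power is ordinarily quoted for the numeric rule alone. This is fair as to practice. Closing a cohort for poor risk-benefit is also not simply a false negative on activity. What remains is that 9.3.6 writes the judgement as a requirement for continuing, while 9.1 makes continuation automatic.

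A reader might infer three stronger things that the text does not support:

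- That the 10% bar contradicts the 2-of-12 rule. As an observed rate in 12 it is the same cut-off.
- That power has been shown to fall to 81% or 72%. Those values depend on assumed refusal or recording probabilities.
- That the gate threatens false-positive control or makes closed cohorts uninterpretable. It lowers type I error, and section 9.3.2 still provides the response rate with an exact 95% interval.

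**Conclusion.** The point holds as an inconsistency between two current sections, worth correcting but not a failure of the design. Sections 9.1 and 9.3.6 give different conditions for stage 2. For tdMeta cohorts, one of the added conditions uses an undefined measure that is either redundant (if ORR) or impossible to apply as written (if anything else). The sponsor condition applies to all cohorts and reduces power and type I error by an amount that cannot be obtained from the protocol. The 9.1 figures therefore describe the numeric rule alone.

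The firm numbers are those of the numeric rule: type I error 0.0052 and power 90.1% at 6 or more of 35, against 0.001 and 88% stated. This gap exists without the extra gate and is not caused by it. It rests only on exact binomial sampling and the inputs printed in 9.1. Every power below 90.1% in Steps 3 and 4 is a sensitivity illustration under stated assumptions.

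**What to change.** 1. In 9.3.6 delete the rwRR/10% clause, or replace rwRR with ORR by investigator RECIST 1.1. State the same rule in 9.1 and 9.3.6: stage 2 opens when 2 or more of the first 12 participants respond, on the response definitions in 9.1.
2. Describe closure on the sponsor's risk-benefit judgement separately, as a documented and non-binding reason to close a cohort and not as part of the counting rule.
3. In 9.1 say that the operating characteristics assume continuation whenever 2 or more of 12 respond. Then either restate them for the printed cut-off (6 or more of 35: type I error 0.0052, power 90.1%) or reconcile the cut-off with the stated figures (7 or more of 35: 0.0012 and 87.5%). Attaching the continuation assumption to the existing 88% would not be enough.

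The cost is protocol wording in two sections, with no change to the planned 12 and 35. The sponsor has less room to close a cohort without recording why and, if the cut-off of 6 is kept, must report a less favourable type I error.

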9.3.7 LIMITATIONS OF ANALYSES

The enrolled participants will be assigned to study cohorts based on molecular group status with hypothesized anti-tumor benefit. Consequently, any exploratory analyses for additional biomarker associations will be based on a potentially biased subset of the overall population. Statistical methodology will consider this potential bias.

10 QUALITY ASSURANCE AND QUALITY CONTROL

10.1.1 CLINICAL MONITORING

Clinical site monitoring is conducted to ensure that the rights and well-being of participants are protected, that the reported trial data are accurate, complete, and verifiable, and that the

The information contained in this protocol and all other information relevant to this study are confidential and proprietary information of Strata Oncology Inc., except as may be required by federal, state or local laws or regulation, and may not be disclosed to others without prior written permission of Strata.

Page 48 of 56

conduct of the trial is in compliance with the currently approved protocol/amendment(s), with ICH/GCP, and with applicable regulatory requirement(s).

- Monitoring for this study will be performed by the study sponsor or designee.
- A combination of on-site and remote monitoring will be used for this study. Targeted/risk-based monitoring will be used to assess safety and key variables and verify endpoints.
- Details of clinical site monitoring are documented in a Clinical Monitoring Plan (CMP). The CMP describes in detail who will conduct the monitoring, at what frequency monitoring will be done, at what level of detail monitoring will be performed, and the distribution of monitoring reports.
- Independent audits may be conducted by Strata Oncology to ensure monitoring practices are performed consistently across all participating sites and that monitors are following the CMP.

10.1.2 QUALITY ASSURANCE AND QUALITY CONTROL

Each clinical site will perform internal quality management of study conduct, data and biological specimen collection, documentation, and completion. The investigational site will provide direct access to all trial related sites, source data/documents, and reports for the purpose of monitoring and auditing by the sponsor, and inspection by local and regulatory authorities. Quality control (QC) procedures will be implemented beginning with the data entry system and data QC checks that will be run on the database will be generated. Any missing data or data anomalies will be communicated to the site(s) for clarification/resolution.

Following written Standard Operating Procedures (SOPs), the monitors will verify that the clinical trial is conducted, data are generated, and biological specimens are collected, documented (recorded), and reported in compliance with the protocol, ICH/GCP, and applicable regulatory requirements.

11 ETHICS/PROTECTION OF HUMAN PARTICIPANTS

11.1 INFORMED CONSENT PROCESS

Prior to the beginning of the trial, the investigator will ensure the IRB's written approval for the protocol and written ICF(s) as well as any other written information to be provided to the participants. The investigator must comply with applicable regulatory requirements (e.g., 45 CFR Part 46, 21 CFR Part 50, 21 CFR Part 56) and must adhere to ICH GCP.

The investigator is responsible for obtaining written informed consent from each participant enrolled in the trial. The investigator or designee must explain the study objectives, methods, and potential benefits and potential risks of study participation. Participants will also be informed

The information contained in this protocol and all other information relevant to this study are confidential and proprietary information of Strata Oncology Inc., except as may be required by federal, state or local laws or regulation, and may not be disclosed to others without prior written permission of Strata.

Page 49 of 56

by the investigator or designee that they may withdraw from the study at any time for any reason. Original, signed consent forms will be maintained at the site and will be made available for inspection, as needed.

11.1.1 CONSENT/ASSENT AND OTHER INFORMATIONAL DOCUMENTS PROVIDED TO PARTICIPANTS

The ICF describes in detail the study intervention, study procedures, risks, and benefits to study participation as well as a statement informing the participant of their right to withdraw from the study at any time for any reason. Written informed consent is required prior to starting intervention/administering study intervention.

11.1.2 CONSENT PROCEDURES AND DOCUMENTATION

Informed consent is a process that is initiated prior to an individual agreeing to participate in the study and continues throughout study participation. Consent forms will be IRB approved and the participant will be asked to read and review the document. The investigator will explain the research study to the participant and answer any questions that may arise. A verbal explanation will be provided in terms suited to the participant's comprehension of the purposes, procedures, and potential risks of the study and of their rights as research participants. A translated version of the ICF will be provided in the participant's primary language, as applicable. Participants will have the opportunity to carefully review the written consent form and ask questions prior to signing. The participants should have the opportunity to discuss the study with their family or surrogates or think about it prior to agreeing to participate. The participant will sign the ICF prior to any procedures being done specifically for the study. Participants must be informed that participation is voluntary and that they may withdraw from the study at any time, without prejudice. A copy of ICF will be given to the participants for their records.

The informed consent process will be conducted and documented in the source document (including the date of consent), and the form signed, before the participant undergoes any study-specific procedures. The rights and welfare of the participants will be protected by emphasizing to them that the quality of their medical care will not be adversely affected if they decline to participate in this study.

11.2 STUDY DISCONTINUATION AND CLOSURE

The study may be temporarily suspended or prematurely terminated if there is sufficient reasonable cause. Written notification, documenting the reason for study suspension or termination, will be provided by the suspending or terminating party to all study participants, investigators, funding agency, sponsor, and regulatory authorities, as applicable. If the study is prematurely terminated or suspended, the PI will promptly inform study participants, the IRB,

The information contained in this protocol and all other information relevant to this study are confidential and proprietary information of Strata Oncology Inc., except as may be required by federal, state or local laws or regulation, and may not be disclosed to others without prior written permission of Strata.

Page 50 of 56

and sponsor and will provide the reason(s) for the termination or suspension. Study participants will be contacted, as applicable, and be informed of changes to study visit schedule.

Circumstances that may warrant termination or suspension include, but are not limited to:

- Determination of unexpected, significant, or unacceptable risk to participants
- Demonstration of efficacy that would warrant stopping
- Insufficient compliance to protocol requirements
- Data that are not sufficiently complete and/or evaluable
- Determination that the primary endpoint has been met
- Determination of futility

The study may resume once concerns about safety, protocol compliance, and data quality are addressed, and satisfy the sponsor, IRB and/or FDA and/or applicable regulatory bodies.

